5 TRIAL POPULATION

5.1 Screening population

All infants born at 33 0/7 to 35 6/7 weeks gestation and ≥ 1500 grams are screened for study entry if they are admitted to the NICU with an admitting diagnosis of acute perinatal asphyxia, neonatal depression, encephalopathy and/or fetal acidemia at less than 6 hours of age. All these infants at < 6 hours of age are evaluated by clinical and biochemical criteria and further assessed by neurological examination. Both inborn and outborn infants are evaluated. From this population, babies are screened for inclusion in the trial using the following eligibility criteria.

Eligibility

Inclusion criteria

Infants 33 0/7 to 35 6/7 weeks GA (best obstetrical estimate) and ≥ 1500 grams birth weight (to minimize potential difficulties placing esophageal probe) who meet clinical, biochemical and neurologic criteria for moderate to severe NE in this GA range at ≤ 6 hours age:

1) Biochemical:

Cord gas or if unavailable, blood gas within first hour of life with $\text{pH} \leq 7.00$ or base deficit (BD) ≥ 16 mEq/L, OR

2) Clinical in the absence of blood gas results or Clinical with more modest fetal acidemia (cord or 1st hour of life blood gas with a pH of 7.01-7.15 or BD > 10.0 to 15.9mEq/L):

a) Acute perinatal event (e.g., abruptio placenta, cord prolapse, uterine rupture, maternal cardiac or respiratory arrest, severe FHR abnormality such as variable or late decelerations,) AND

b) Requirement for positive pressure ventilation for apnea OR poor respiratory effort since birth for at least 10 minutes OR 10-minute Apgar score ≤ 5

AND

3) Neurologic:

Clinical Seizures OR modified Sarnat score with moderate or severe abnormalities in at least 3 of the 6 categories; at least one must be altered level of consciousness (lethargy or stupor/coma) as determined by a certified examiner.

All infants who meet criteria for potential inclusion should undergo standard neurologic exam as for infants ≥ 36 wks GA being considered for hypothermia, with findings recorded.

Criteria for exclusion in hypothermia trial

1) Receipt of paralytic agent or sufficient sedative or analgesic agent that is considered by the examiner to confound the qualifying neurologic exam

2) Etiology of NE not likely to be hypoxic-ischemic in origin

3) Major congenital anomaly that may confound outcome

4) Considered to be moribund and will not be receiving full intensive care

- 5) Equipment and/or appropriate staff not available
- 6) Infant was cooled prior to arrival at the NRN center and had a core temperature <34.0° C for more than 1 hour at the time of screening (Cooling on transport is to be discouraged, in general)
- 7) Unable to randomize by 6 hours of age
- 8) Infant to receive or receiving ECMO
- 9) All blood gases (cord and neonatal at <1 hour of age) have a pH >7.15 and a base deficit <10 mEq/L
- 10) Consent not obtained from parent(s)
- 11) Concurrence not provided by responsible attending neonatologist

5.2 Withdrawal / Follow-up

- Infants can be lost-to-follow-up between Network Status (120 days after birth, or time of discharge/transfer) and the time of the scheduled 18-22-month follow-up visit (although the Covid pandemic did require some subjects to undergo follow-up at later dates). The Premie Hypothermia PH13 form is completed at the time of network status. Infants cannot be lost prior to network status.
- Infants who withdraw from the study will not have any data collected beyond the timepoint of withdrawal. Data collected prior to withdrawal will be available for summarization and analysis.
- Numbers of infants who withdraw or are lost to follow-up will be presented in the CONSORT diagram.

5.3 Baseline Patient Characteristics

Baseline characteristics will be compared across treatment groups. Table 1 in the MockTablesAppendix.docx document lists out maternal and neonatal characteristics that will be summarized in the primary published paper. In addition to the variables indicated in Table 1 of the MockTablesAppendix.docx document, other baseline characteristics may be investigated internally by the Premie Hypothermia Subcommittee. For programming purposes, the following list contains an example list of infant and maternal characteristics that will or may be investigated as well as dataset and variable names needed to locate the characteristics in the clinical database:

- Infant baseline characteristics (*Variable Type, Form, Variable name in clinical database*)
 - Birth year (*Multiple level discrete, PH05: A.1.a, PH5BRTDT*)
 - GA (*Multiple level discrete – at level of weeks, PH05: A.7.a, PH5GESTW*)
 - Sex (*Binary, PH05: A.8, PH5SEX*)
 - Birthweight (grams) (*Continuous, PH05: A.4, PH5BRTWT*)
 - Length (cm) (*Continuous, PH05: A.5, PH5BRTLN*)
 - Head circumference (cm) (*Continuous, PH05: A.6, PH5HCIRC*)
 - Seizures (*Binary, PH02: C.1, PH2SIEZ*)
 - Level of Encephalopathy (*Binary, PH02: G.4, PH2LECEP*)
 - Inborn/outborn status (*Binary, PH05: A.2, PH5OUTBN*)
 - 1-minute Apgar scores (*Continuous, PH05: A.3.a, PH5APG1*)

- 5-minute Apgar scores (*Continuous, PH05: A.3.b, PH5APG5*)
- Received resuscitation at delivery (*Binary, PH05: B.1-B.5, PH5OXYG / PH5BAGM / PH5CHCOM / PH5INTUB / PH5DRUGS. any equal to 'Y'*)
 - Types of resuscitation (*Multiple level discrete or individual binary, use PH05: B.1-B.5, PH5OXYG / PH5BAGM / PH5CHCOM / PH5INTUB / PH5DRUGS.*)
- Received resuscitation at 10 minutes (*Binary, PH05: C.1-C.5, PH5OXY10 / PH5BAG10 / PH5CHE10 / PH5INT10 / PH5DRG10. Any equal to 'Y'*)
 - Types of resuscitation (*Multiple level discrete or individual binary, use PH05: C.1-C.5, PH5OXY10 / PH5BAG10 / PH5CHE10 / PH5INT10 / PH5DRG10.*)
- Received cord blood gas (*Binary, PH05: E.1, PH5CBGO, will be used in the construction of a derived variable containing cord blood gas information if non-missing and <1 hour of age information if cord blood gas information is missing and <1 hour of age information is non-missing. Stated another way: select cord gas if both cord gas and 1 hr gas are available and select 1 hr gas if cord not available. These variables are an intermediate step. See cord or postnatal variables below for variables that will actually get used in reports.*)
 - Source (*Multiple level discrete, PH05: E.1.a, PH5CBS*)
 - pH (*Continuous, PH05: E.1.b, PH5CBPH*)
 - PCO₂ (mmHg) (*Continuous, PH05: E.1.c, PH5CBPCO*)
 - PO₂ (mmHg) (*Continuous, PH05: E.1.d, PH5CBP02*)
 - HCO₃ (mEq) (*Continuous, PH05: E.1.e, PH5CBHCO*)
 - Base deficit (*Continuous, PH05: E.1.f, PH5CBBD*)
- Postnatal blood gas obtained at <1 hour of age (*Binary, PH05: E.2, PH5PNBGO, will be used in the construction of a derived variable containing cord blood gas information if non-missing and <1 hour of age information if cord blood gas information is missing and <1 hour of age information is non-missing. Stated another way: select cord gas if both cord gas and 1 hr gas are available and select 1 hr gas if cord not available. These variables are an intermediate step. See cord or postnatal variables below for variables that will actually get used in reports*)
 - Source (*Multiple level discrete, PH05: E.2.a, PH5PGS*)
 - pH (*Continuous, PH05: E.2.d, PH5PGPH*)
 - PCO₂ (mmHg) (*Continuous, PH05: E.2.e, PH5PGPCO*)
 - PO₂ (mmHg) (*Continuous, PH05: E.2.f, PH5PGPO2*)
 - HCO₃ (mEq) (*Continuous, PH05: E.2.g, PH5PGHCO*)
 - Base deficit (*Continuous, PH05: E.2.h, PH5PGBD*)
- Cord or postnatal (<1 hour of age) blood gas (*Combination of appropriate blood gas variables from the above two blood gas groups. Use Cord variable if non-missing and use <1 hour variable if cord variable is missing and <1 hour variable is non-missing. Stated another way: select cord gas if both cord gas and 1 hr gas are available and select 1 hr gas if cord not available. These variables will actually be the variables used in reports covering cord or postnatal blood gas.*)
 - pH (*Continuous*)
 - PCO₂ (mmHg) (*Continuous*)
 - PO₂ (mmHg) (*Continuous*)
 - HCO₃ (mEq) (*Continuous*)

- Base deficit (*Continuous*)
- Maternal baseline variables
 - Mother's age (*Continuous, PH04: A.1, PH4MAGE*)
 - Mother's race (*Multiple level discrete, PH04: A.2, A.2.a.1-A.2.a.3, PH4MRACE, PH4MRAC1, PH4MRAC2, PH4MRAC3*)
 - Ethnicity (*Multiple level discrete, PH04, A.3, PH4METHN*)
 - Marital status (*Binary, PH04: A.4, PH4MARST*)
 - Education status (*Multiple level discrete, PH04: A.5, PH4EDSTA*)
 - Parity (*Multiple level discrete, PH04: A.6.b, PH4PARIT*)
 - Multiple Birth (*Binary, PH04: A.7, PH4MLTIB*)
 - Prenatal care (*Binary, PH04: A.8, PH4PRECR*)
 - Medical insurance (*Multiple level discrete, PH04: A.9, PH4INSUR*)
 - Complications during pregnancy (*Binary, PH04: B.1-B.4, PH4HYPRE / PH4ANTHM / PH4THYRM / PH4DIABT. any equal to 'Y'*)
 - Hypertension/pre-eclampsia/eclampsia (*Binary, PH04: B.1, PH4HYPRE*)
 - Antepartum hemorrhage (*Binary, PH04: B.2, PH4ANTHM*)
 - Thyroid malfunction (*Binary, PH04: B.3, PH4THYRM*)
 - Diabetes (*Binary, PH04: B.4, PH4DIABT*)
 - Complications at delivery (*Binary, PH04: D.1 through D.14, PH4DEFHT, PH4CORDM, PH4CORDO, PH4UTRPT, PH4SHDYS, PH4PLACP, PH4PLACO, PH4MATHM, PH4MAFEH, PH4MATTR, PH4MATCR, PH4MATSZ, PH4PYREX, PH4CHORI, PH4HISCH, PH4ANTIB. any equal to 'Y'*)
 - Decelerations and/or loss of fetal heart tones (*Binary, PH04: D.1, PH4DEFHT*)
 - Cord mishap (*Binary, PH04: D.2, PH4CORDM*)
 - Cord mishap, type (*Multiple level discrete, PH04: D.2.a-D.2.d, PH4CORD1 / PH4CORD2 / PH4CORD3 / PH4CORD4 / PH4CORDO*)
 - Uterine rupture? (*Binary, PH04: D.3, PH4UTRPT*)
 - Shoulder dystocia? (*Binary, PH04: D.4, PH4SHDYS*)
 - Placental problems? (*Binary, PH04: D.5, PH4PLACP*)
 - Placental problems, type (*Multiple level discrete, PH04: D.5.a-D.5.dPH4PLAC1 / PH4PLAC2 / PH4PLAC3 / PH4PLAC4*)
 - Maternal hemorrhage? (*PH04: D.6, PH4MATHM*)
 - Maternal-fetal hemorrhage? (*PH04: D.7, PH4MAFEH*)
 - Maternal trauma? (*PH04: D.8, PH4MATTR*)
 - Maternal cardio-respiratory arrest? (*PH04: D.9, PH4MATCR*)
 - Maternal seizures? (*PH04: D.10, PH4MATSZ*)
 - Pyrexia ≥ 37.6 ? (*PH04: D.11, PH4PYREX*)
 - Documented chorioamnionitis? (*PH04: D.12, PH4CHORI*)
 - Antibiotic for suspected/confirmed infection? (*PH04: D.14, PH4ANTIB*)
 - Rupture of membranes (*Binary, PH04: E.1, PH4RUPT*)
 - Duration of rupture of membranes (*Continuous, birth date as date/time variable {PH05: A.1.a + A.1.b, PH5BRTDT and PH5BRTTM} minus date/time of rupture of membranes: PH04: E.1.a + E.1.b, PH4RUPDT and PH4RUPTM*)

- Duration of rupture of membranes, ≤ 18 hr (Binary, based on duration of rupture of membranes)
- Mode of delivery (*Multiple level discrete, PH04: F.1, PH4FNMOD*)

Note: The amount of missing data will be indicated in the Tables.

6 STATISTICAL ANALYSIS

6.1 Primary Efficacy Outcome

The primary outcome will be death or moderate to severe disability at 18-22 months corrected age (or later as required by Covid pandemic) (*Binary*).³ Death will be identified by finding an indication of death on the PH13 network status form, PH15 adverse event form, DEATH_FU and DEATH_NEW variables from the follow-up (FU) analysis dataset, JFSTATUS = 3 from the FU analysis dataset.⁴

The presence or absence of disability will be determined by the standard NRN interdisciplinary follow-up exam. Where possible, the primary outcome values will be taken from the FU analysis dataset. Binary variables for severe, moderate, mild, and no disability will be created using the following criteria. A single binary moderate or severe disability variable will be created from this individual disability severity variable to identify infants with moderate or severe disability (= 1, if severe disability or moderate disability is indicated; = 0, if disability can be determined and not equal to severe or moderate.)

Severe disability will be defined by the presence of any of the following:

- a Bayley III cognitive score < 70 (*FU: B3_COG70*),
- Gross Motor Functional Classification Status (GMFCS) Level of 3-5 (*FU:GMF_LEV >= 3*),
 - Note: The GMF_LEV variable will need to be programmed in accordance with GMF_LEV as programmed in the regular RTI FU (follow-up) analysis dataset.
- blindness (visual acuity $< 20/200$ in the both eyes as determined by an ophthalmologist) (*FU: VISIONR and FU:VISIONL equal to 4 or 5, B.1.e*) or
- profound hearing loss (inability to understand commands despite placement of a cochlear implant or amplification) (*FU:HEARIMP = 1 (B.2.b) and FU:HEARAID = 1, 2, or 3 (B.2.b.1) and FU:HEARCOC = 1, 2, or 3 (B.2.b.2)*).

Moderate disability will be defined by:

³ The primary outcome calculation contains variables that are only available in the Premie Hypothermia Follow-up Database. When programming the primary outcome and other outcomes derived from the Premie Hypothermia Follow-up database, you may come across outcomes that are missing. If outcomes are missing, determine what variable in the derivation is causing the missingness and then review data, regarding the infant with a missing outcome, from the PF11, PF12, and PF09A forms. The PF11 form will tell you if particular data is available, and the PF12 form will have information about lost-to-follow-up and additional information that may help understand the condition of the infant. Review the data in these forms to better understand why the data is missing and document what you find in a text file.

⁴ In this SAP, FU refers to the Premie Hypothermia FU database.

- a Bayley III cognitive score between 70-84 (*FU.B3_COG70 = 0 and FU.B3_COG85 = 1*) and either
- a GMFCS level of 2 (*FU.GMF_LEV = 2*), or
- an active seizure disorder requiring ongoing anticonvulsant therapy and not attributable to another disease process (*PH02: C.1, PH2SIEZ = 'Y' or PF04 A.4 = 'Y'*), or
- a hearing deficit requiring amplification or cochlear implant to understand commands (*FU.HEARCOG = 1,2, or 3 or FU.HEARAID = 1, 2, or 3*).

Mild disability will be defined by:

- a cognitive score 70-84 (*FU.B3_COG70 = 0 and FU.B3_COG85 = 1*), or
- a cognitive score ≥ 85 (*FU.B3_COG70 = 0 and FU.B3_COG85 = 0*) and
- any of the following:
 - GMFCS level I (*FU.GMF_LEV = 1*),
 - seizure disorder (*PH02: C.1, PH2SIEZ = 'Y'*) or
 - hearing loss not requiring amplification (*FU:HEARIMP = 1 (B.2.b) and FU:HEARAID = 0 and FU:HEARCOG = 0 (B.2.b.2)*).

Normal will be defined by:

- a cognitive score ≥ 85 (*B3_COG70 = 0 and B3_COG85 = 0*) and
- the absence of any neurosensory deficits (*PH02 Q C.1. = 'N', FU.GMF_LEV = 0, FU.BLIND_06 = 0, FU.DEAF_06=0, FU.HEARAID=0, FU.HEARCOG = 0, FU.HEARIMP=0*)).

In addition to the above 4 levels of disability, a separate disability variable will be created to identify infants who have “Profound disability”. Profound disability will be indicated by the assignment of lowest possible Bayley score due to inability to test due to severity of impairment. Note: any infant with the profound disability variable equal to yes will also have the primary outcome variable equal to yes, since profound disability is a subclass of severe disability with respect to the primary outcome.

Although the Bayley III cognitive score is thought to systematically give higher scores at 18-22 months than the Mental Developmental Index of the Bayley II used in the original NRN hypothermia trial for infants ≥ 36 weeks GA, this is likely to affect both study groups in this study similarly. Bayley III was used for the Optimizing Cooling Strategies RCT. Please note that the follow-up for this trial is at 18-22 months corrected age in keeping with all previously performed RCTs of hypothermia for HIE in newborn infants 36 weeks gestation or beyond, although the Covid pandemic required some visits to be deferred to later times.

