4.3 Analysis Datasets

This analysis will use two analysis populations, a full analysis set (FAS) and per-protocol (PP).² The FAS analysis population will include all randomized infants with ascertained primary outcomes. This FAS analysis population is recognized as being as close as possible to an intent-to-treat population. All analyses based on the FAS will analyze infants as randomized. The PP analysis population will include all infants who received their randomized treatment (72 hours of hypothermia or normothermia) and have a determined primary outcome. All analyses based on the PP will analyze infants as treated.

² ICH E9: <https://www.fda.gov/regulatory-information/search-fda-guidance-documents/e9-statistical-principles-clinical-trials>

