6.5.5 Final Analysis

The final analysis will occur after 168 infants have completed the trial, as specified earlier. The final analysis will not occur until all enrolled infants have a primary outcome determination, i.e. have the primary endpoint value assigned, classified as withdrawn without primary outcome assigned, or deemed lost to follow-up. Part of determining primary outcome of enrolled infants will involve masked adjudication of outcomes for infants who have an indeterminable outcome based on partially collected follow-up information. Once all enrolled infants have reached final status and primary endpoints determined, the clinical database will be exported, and study analysis datasets created. At that point, the analysis datasets will be considered “locked” and any further adjustments to the clinical datasets will not be included in the analysis datasets.

The final analysis will involve posterior distribution estimation for the effect of hypothermia relative to normal cooling. For binary outcomes, the effect will be the adjusted relative risk and adjusted risk differences calculated from a binomial regression model with logit link and post processing of

predicted outcome probabilities. For count outcomes, the effect will be the adjusted relative risk from the two groups obtained using negative binomial regression. For ordinal outcomes, the effect will be the adjusted odds ratio calculated from the cumulative logits.

For treatment relative risk estimation, posterior probabilities of >0%, >5%, >10% and >20% decrease in binary outcomes will be calculated. If θ is the relative risk defined as risk in cooling group over risk in control group, then the above specified posterior probabilities are, $\Pr(\theta < 1 | X)$, $\Pr(\theta < 0.95 | X)$, $\Pr(\theta < 0.9 | X)$, $\Pr(\theta < 0.8 | X)$. In addition to posterior probability calculations, graphical displays of the posterior distribution and appropriate 95% credible intervals for the over-all relative risk will be created. Finally, forest plots of the center level relative risks and 95% credible intervals will be created.

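### The four disability classes in SAP 6.1 are neither exhaustive nor mutually exclusive, so the primary outcome of some fully examined survivors is left open between 0 and missing

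*SAP*

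**What the plan says.** Section 6.1 builds the disability part of the primary outcome from four classes.

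- **Severe** includes "Gross Motor Functional Classification Status (GMFCS) Level of 3-5", a cognitive score below 70, blindness, or profound hearing loss. The hearing criterion is coded as an impairment with both the aid and the implant variable positive.
- **Moderate** opens with "a Bayley III cognitive score between 70-84", joined by the words *and either* to the alternatives that follow: "a GMFCS level of 2 (*FU.GMF_LEV = 2*), or" an active seizure disorder, or "a hearing deficit requiring amplification or cochlear implant to understand commands".
- **Mild** is a score of 70-84, or a score of at least 85 with GMFCS level 1, a seizure recorded on form PH02, or hearing loss with aid and implant both 0.
- **Normal** is a score of at least 85 with GMFCS 0, no PH02 seizure, no blindness, and no hearing loss, aid or implant.

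The binary moderate/severe variable is derived from the severity classification. It is 1 for severe or moderate and "0, if disability can be determined and not equal to severe or moderate".

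Section 4.3 states: "The FAS analysis population will include all randomized infants with ascertained primary outcomes". Section 6.6 rules out imputation. Section 6.5.5 provides "masked adjudication of outcomes for infants who have an indeterminable outcome based on partially collected follow-up information". Section 6.4 reports a four-level disability outcome in survivors and a separate binary outcome for each level.

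**The concern.** A derivation rule for a primary endpoint should give each fully observed child exactly one value. This one fails in two ways.

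First, GMFCS level 2 and aided hearing count towards moderate only when the cognitive score is 70-84. At 85 or above, mild stops at GMFCS 1 and unaided loss, and normal excludes both findings. A child with either finding and a score of 85 or more can be left with no class although nothing is missing. Two competent programmers could then code the same child 0 or missing and obtain different denominators for the full analysis set.

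Second, no order of precedence is stated, and a score of 70-84 is enough for mild. Separate binary flags coded as written would therefore count moderate children, and severe children scoring 70-84, as mild as well. That over-counts mild disability among survivors.

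Treatment is unmasked (section 3.1). A coding choice made after the data are seen would be hard to defend.

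**Working it through.** The SAP gives no figure to reproduce here. The check is to code the section 6.1 rules literally and count the classes that each complete profile meets.

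**Rules as coded**

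| Class | Condition |
|---|---|
| Severe | score <70, or GMFCS ≥3, or blind, or aid and implant both positive |
| Moderate | score 70-84 and (GMFCS 2, or seizure on PH02 C.1 or PF04 A.4, or aid, or implant) |
| Mild | score 70-84; or score ≥85 and (GMFCS 1, or PH02 C.1 seizure, or unaided hearing loss) |
| Normal | score ≥85, GMFCS 0, PH02 C.1 = N, not blind, no hearing loss, aid or implant |

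The implant variable is spelled HEARCOC under severe and HEARCOG elsewhere; both are taken as the same variable.

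**Profiles.** Score band (3) × GMFCS 0-5 (6) × PH02 seizure (2) × PF04 seizure (2) × hearing: none, unaided loss, aid, implant, both (5) × blindness (2) = 720, or 240 per score band.

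**Gap, score ≥85**

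- Not severe: GMFCS 0-2 (3) × PH02 (2) × PF04 (2) × hearing other than both (4) × not blind (1) = 48.
- Moderate: none, because the score condition fails.
- Of the 48, not mild: GMFCS 0 or 2 (2) × PH02 = N (1) × PF04 (2) × hearing none, aid or implant (3) = 12.
- Of the 12, normal: GMFCS 0 with no hearing finding × PF04 (2) = 2.
- No class: 12 − 2 = **10**.

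The 10 are GMFCS 2 with no hearing finding, an aid alone or an implant alone, and GMFCS 0 with an aid alone or an implant alone, each with PF04 A.4 yes or no. The other two score bands have no gap: below 70 is always severe, and 70-84 is always at least mild.

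Nearby profiles with a score ≥85 are classified. GMFCS 2 with a PH02 seizure, GMFCS 2 with unaided loss, an aid with GMFCS 1, and an aid with a PH02 seizure are all mild. Aid and implant together are severe.

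**Overlap, score 70-84**

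- Not severe: 48 profiles by the same product. Without any moderate feature: GMFCS 0 or 1 (2) × no seizure on either form (1) × hearing none or unaided (2) = 4. Moderate: 48 − 4 = **44**, and all 44 also meet mild.
- Severe: 240 − 48 = 192, and all of these also meet mild.

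These are counts of combinations, not of children, and 10/720 is not a probability.

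**What a few children could do (illustration only).** Assume 84 per arm (168/2, section 3.4), with 59 events on normothermia and 42 on hypothermia (about 70% and 50%, the rates in section 3.4). The number of gap children is assumed. With all of them coded 0, RR = (42/84)/(59/84) = 0.712.

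| Gap children (hypothermia, normothermia) | Dropped | Coded 1 |
|---|---|---|
| 3, 0 | (42/81)/(59/84) = 0.738 | 45/59 = 0.763 |
| 0, 3 | (42/84)/(59/81) = 0.686 | 42/62 = 0.677 |
| 3, 3 | (42/81)/(59/81) = 0.712 | 45/62 = 0.726 |

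With 3 per arm dropped, the RR is unchanged and the risk difference moves from −17/84 = −0.202 to −17/81 = −0.210.

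**The case against.** A reader might infer that these children necessarily fall out of the full analysis set. The SAP does not say so. Every severe and moderate item has been measured and is negative, so 0 is a natural reading of the binary rule. Section 6.5.5 also holds the final analysis until each infant has an endpoint value, is withdrawn without one, or is lost to follow-up. A fully examined child is neither withdrawn nor lost, which points towards assigning a value. Footnote 3 to section 6.1 makes the programmer trace and document any missing outcome, so the case would probably be noticed. All of this stands against certain exclusion. It does not settle the coding: the binary variable is created from the severity variable, for which this child has no value, the footnote gives no assignment rule, and adjudication is described only for partial follow-up.

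A reader might also infer a known bias in the RR, or that such survivors are common. The documents give no count and no imbalance between arms. With equal numbers dropped in equal-sized arms, the RR does not move.

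On overlap, the primary composite is unaffected, because it is 1 whenever severe or moderate is met. Section 6.4 describes a single multi-level variable, which implies one level per child. That softens the point, but section 6.1 also calls for separate binary variables and states no precedence.

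Finally, placing GMFCS 2 and aided hearing in mild may look like the obvious repair. The SAP lists both under moderate, and whether the joining words of that definition are intended cannot be settled from the SAP alone.

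**Conclusion.** The point holds as a defect in the stated rule. On the literal wording, 10 of 720 complete profiles meet no class. All have a score of at least 85, no PH02 seizure and no blindness, with GMFCS 2, or an aid alone or implant alone. For these the SAP leaves the primary outcome open between 0 and missing. In addition, all 44 non-severe moderate profiles and all 192 severe profiles scoring 70-84 also satisfy mild. This threatens the disability tables but not the primary composite.

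The conclusion rests on the conditions as printed and on reading 70-84 alone as sufficient for mild. The number of affected children is unknown, so the effect on the RR or the risk difference cannot be stated. The shifts shown depend wholly on assumed counts.

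**What to change.** Before database lock and without reference to treatment arm:

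1. Derive one severity variable by strict hierarchy: severe, else moderate, else mild, else normal. Build every disability outcome in section 6.4 from it.
2. Reconcile the joining wording of the moderate definition with the protocol, and assign the unclassified profiles to one named class.
3. State that a survivor with all severe and moderate items measured and none met has binary outcome 0 and stays in the full analysis set. If step 2 brings these profiles under moderate, they are events and this rule does not apply to them.
4. If the moderate definition stands as written, report one sensitivity run that counts these children as moderate.
5. Use one spelling for the implant variable.

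The cost is a short SAP amendment, a few lines of derivation code and at most one extra model run. No new data are needed.

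### Section 6.1 codes an active, treated seizure disorder with the enrolment seizure flag, so entry seizures alone can make a survivor scoring 70-84 a primary event

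*SAP*

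**What the plan says.** Section 6.1 bases disability on follow-up: "The presence or absence of disability will be determined by the standard NRN interdisciplinary follow-up exam". It adds: "Where possible, the primary outcome values will be taken from the FU analysis dataset". Moderate disability requires a cognitive score of 70-84 together with GMFCS level 2, a seizure criterion or a hearing criterion. The seizure criterion reads "an active seizure disorder requiring ongoing anticonvulsant therapy and not attributable to another disease process (*PH02: C.1, PH2SIEZ"; the code sets it to yes when that PH02 item is 'Y' or when PF04 A.4 is 'Y'.

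Section 5.3 lists the same PH02 item among the infant baseline characteristics: "Seizures (*Binary, PH02: C.1, PH2SIEZ". The neurologic entry criterion in Section 5.1 is "Clinical Seizures OR modified Sarnat score with moderate or severe abnormalities" in at least three of six categories. Section 6.4 describes PF04 A.4 as seizures since discharge.

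The PH02 item recurs in two other classes. Mild uses "seizure disorder (*PH02: C.1, PH2SIEZ". Normal requires "the absence of any neurosensory deficits (*PH02 Q C.1" to be 'N', along with the other neurosensory items. Neither uses PF04 A.4. The binary disability variable is 1 for moderate or severe, and "0, if disability can be determined and not equal to severe or moderate".

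**The concern.** A seizure recorded at enrolment, before treatment, cannot show that a child has an active seizure disorder on anticonvulsants at 18-22 months. As coded, it is nevertheless enough to complete the moderate definition for a child scoring 70-84, and so to set the primary outcome to 1. The flag can only turn non-events into events.

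The secondary outcome of survival with no disability is wrong in both directions. An otherwise normal survivor with entry seizures cannot be normal. A child scoring 85 or more whose only positive item is seizures since discharge is coded normal.

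Two other parts of the plan are touched. The Section 6.5.8 subgroup of infants who qualified on seizures alone would, if they carry the flag as the entry rule implies, have every survivor scoring 70-84 counted as an event by construction. Baseline seizures, a candidate adjustment covariate under Sections 5.3 and 6.5.7, would partly define the outcome being modelled.

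**Working it through.** The SAP states no figure for this point, so there is none to reproduce. The check has two parts.

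**1. The coded rule.** Take a survivor scoring 70-84 with GMFCS 0, no hearing deficit and no severe criterion.

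| PH02 C.1 (entry) | PF04 A.4 (since discharge) | Class as coded | Class without PH02 C.1 |
|---|---|---|---|
| N | N | mild | mild |
| N | Y | moderate | moderate |
| Y | N | **moderate (primary = 1)** | **mild (primary = 0)** |
| Y | Y | moderate | moderate |

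Enumerating all combinations gives 3 cognitive bands x 4 GMFCS groups x 5 hearing states x 2 vision x 2 entry seizure x 2 seizure since discharge = 480 profiles (profiles, not infants).

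- If 70-84 is required together with any one of the three further criteria, 4 profiles are primary events only through the entry flag. All score 70-84 with GMFCS 0-1 and no device.
- If 70-84 is tied only to GMFCS 2, and seizure or hearing each suffices alone, 10 profiles flip.

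The mismatch exists under either reading. Under the first, all 44 non-severe moderate profiles also meet mild, and 10 profiles meet no class (for example, score 85 or more, GMFCS 2, no entry seizures).

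**2. Illustrative size.** From Section 3.4: 168 infants, taken as 84 per arm, and the scenario of 70% (control) vs 50% (cooled). Assumed: a share q of true non-events is flipped. The observed risk is p + (1 - p)q.

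| q control / cooled | Observed risks | RR | RD |
|---|---|---|---|
| 0 / 0 | 0.700 vs 0.500 | 0.714 | -0.200 |
| 5% / 5% | 0.715 vs 0.525 | 0.734 | -0.190 |
| 10% / 10% | 0.730 vs 0.550 | 0.753 | -0.180 |
| 5% / 10% | 0.715 vs 0.550 | 0.769 | -0.165 |
| 10% / 5% | 0.730 vs 0.525 | 0.719 | -0.205 |
| 10% / 3% | 0.730 vs 0.515 | 0.705 | -0.215 |

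Infants flipped at equal q:
- 5%: 84 x 0.30 x 0.05 = 1.3 control and 84 x 0.50 x 0.05 = 2.1 cooled, together 3.4.
- 10%: 2.5 and 4.2, together 6.7.

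Direction: RD is unchanged when 0.50 x q(cooled) = 0.30 x q(control), a ratio of 0.60. RR is unchanged at a ratio of 0.60 x 0.714 = 0.43. Below these ratios the benefit is exaggerated; above them it is diluted.

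Plausibility of q: if 25% of non-events score 70-84, q of 5-10% needs 20-40% of those children to have entry seizures and no other criterion. It needs 33-67% if 15% score 70-84, and 14-29% if 35% do. All these shares are assumed.

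A second illustration multiplies 168 by assumed survival (70-85%), share of survivors scoring 70-84 (15-25%) and share with entry seizures (10-50%), treated as independent with no other moderate criterion met. It gives 168 x 0.70 x 0.15 x 0.10 = 1.8 up to 168 x 0.85 x 0.25 x 0.50 = 17.8 infants.

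Chance that the posterior probability of RR < 1 reaches 0.80 (84 per arm, neutral prior Normal(0, 0.7072) on the log odds ratio, binomial enumeration with a normal approximation, no center or encephalopathy terms): 96.5%, 95.4% and 94.2% for equal q of 0, 5% and 10%.

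**The case against.** The strongest objection is to the weight given to this. A flip needs survival, a score of 70-84, entry seizures, no other qualifying criterion and no seizures since discharge, all together. No input for q comes from the SAP, and the two illustrations (3.4-6.7 and about 2-18 infants) differ widely. At the assumed 10% equal share, the chance of reaching 0.80 falls only from 96.5% to 94.2%. The entry flag precedes randomisation, so with no treatment effect the flipped shares are equal in expectation. At 70% vs 70% the same calculation gives a chance of a false signal of 17.7% with q = 0 and 17.0% with q = 10%. All of this stands: the size is unanchored, and dilution is the natural expectation. Exaggeration needs clearly unequal shares. These cannot be excluded, because survival with a score of 70-84 arises after randomisation, but nothing in the SAP points to them.

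It can also be said that a follow-up item is already in the code, and that the preference for the FU dataset acts as a source-precedence rule. Neither repairs the rule: an explicit OR lets the baseline flag suffice. Masked adjudication in Section 6.5.5 covers only indeterminable outcomes, and this child's outcome is fully determined. The sensitivity analyses in Section 6.5.7 vary covariates and population, not the endpoint.

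Two points on the remedy are fair. PF04 A.4, as described, does not record ongoing therapy or exclude another disease process either. And an endpoint change in an unmasked trial should be decided without sight of outcomes by arm.

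**Conclusion.** The concern holds. The code for one limb of the primary endpoint does not measure what the definition says, and a programmer following it would count some mild survivors as events with no planned check to reveal it. It must be fixed because of that contradiction, not because a large effect has been shown.

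Under the assumptions of 84 per arm, 70% vs 50% and 5-10% of non-events flipped equally, RR moves toward 1 by 0.020 to 0.039 (0.734 - 0.714; 0.753 - 0.714) and RD toward 0 by 1 to 2 percentage points. That is modest, though Section 6.5.5 reports posterior probabilities at RD thresholds only 1 to 2 points apart. With unequal shares the bias can go either way. The actual number affected can be known only from the data.

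The mild and normal rules do not alter the primary outcome but do misstate survival with no disability. The overlap between moderate and mild, and the profiles with no class, are minor.

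**What to change.** Before the analysis datasets are locked:

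1. Remove PH02 C.1 from the moderate, mild and normal derivations.
2. Use follow-up seizure information: PF04 A.4, plus a follow-up item for current anticonvulsant use if one was collected. The SAP names only medication at discharge (PH13 D.4, Section 6.3).
3. If no such item exists, reconcile the criterion's wording with what PF04 A.4 records, and apply it consistently to mild and normal.
4. Minor: state that the most severe class met takes precedence in the multi-level disability outcome, and confirm that a fully assessed survivor meeting neither the severe nor the moderate definition has primary = 0.

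Decide and document the change without reference to outcomes by arm.

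The cost is SAP wording and derivation code, with revision of any programs already drafted. PF04 A.4 is already named in the SAP. It must be checked whether a follow-up anticonvulsant item was collected, and whether any child with the entry flag lacks PF04 A.4 and would become indeterminable; such a child would fall to the masked adjudication already planned.
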